4.3 Withdrawal of Subjects

All subjects will be included in the primary analysis as dictated by the theory of intention to treat analysis. Patients who decide to withdraw prematurely will be withdrawn and provided the standard of care at Tufts Medical Center.

4.4 Recruitment and Retention

4.4.1 Local Recruitment Methods

All faculty and staff in the Department of Anesthesiology and Perioperative Medicine at Tufts Medical Center will be informed about the study at one of the departmental meetings (see “Departmental Meeting Script”). Once the patients arrive to the pre-operative area, the co-investigator, [name], will meet with the patients and discuss the study with them further. If they agree to participate, informed consent will be obtained.

4.4.2 Study-Wide Recruitment Methods

Is this a multicenter study where subjects will be recruited by methods not under the control of the local Tufts site (e.g., call centers, national advertisements)?

Yes No

4.4.3 Payment

Will subjects receive money, gifts, or any other incentive for participating in this study?

Yes No

4.4.4 Reimbursement

Will subjects be reimbursed for their expenses, such as travel, parking, meals, or any other study related costs?

Yes No

5 Study Design

5.1 Study Timelines

- Study subjects will be participating in the study for a total of 2 days.
- On day 1, study subjects will enroll in the study and undergo anesthesia with application of Tegaderm™ and EyeGard® on the eyelids. Once surgery is complete, the Tegaderm™ and EyeGard® will be removed and photograph will be taken. This will conclude participation in the study on day 1
- On day 2, study subjects will be approached by the co-investigator, [name], and will be given a patient satisfaction survey. Completion of the survey will conclude study subject participation in the study.
- We anticipate that we will be able to enroll 5 subjects per day during weekdays. Given that we plan to recruit 159 study subjects, it will take approximately 2 months to enroll all the study subjects.
- The estimated date for primary analyses will be October-December 2018.

5.2 Procedures

- Is there a placebo control arm?

Yes No

We will perform a prospective, double-blind, randomized controlled trial. Participants will be approached by the co-investigator, [name], on the day of the surgery. The research study will be explained and potential participants will be given an informed consent form to read. After the participant has had adequate time to read through the informed consent form, think about the risks and benefits, and ask questions, he or she will be asked to sign the form if he or she wishes to participate in the study. The informed consent form will then be stored in the principal investigator's locked office. Once a study subject is enrolled, the anesthesia provider, surgical provider, as well as the nurse will be informed that this participant is part of the study. The co-investigator, [name], will then gather baseline patient demographic and clinical data.

Photographs will be taken using a digital camera at an angle parallel to the eyes (such that the camera is facing the patient directly), at a distance of 6 inches from the eyes to the lens of the camera, and will be done in the operating room with all room lights on. The photographs will be taken and cropped in such a way that both eyelids are visible but no other facial features will be recognizable. As such, photographs will not be identifiable. A disposable paper ruler will be used to determine camera distance and then placed on the patient's forehead during photography as a marker of size.

Upon entry into the operating room and prior to induction of anesthesia and prior to administering oxygen, the co-investigator, [name], will ask the study subject to close his or her eyes. The co-investigator will then take a photograph of the eyelids as a baseline assessment. Afterwards, anesthesia will be induced according to standard of care at Tufts Medical Center. Once the anesthesia provider establishes mask ventilation, the co-investigator, [name], will apply the EyeGard® on one eye and the Tegaderm™ on the other eye according to the

randomization schema. The exact time of application will be documented. At the end of the surgery, the co-investigator, [name], will remove the EyeGard® and Tegaderm™. She will then take another photograph of the eyelids and document the time.

On post-op day 1, the co-investigator, [name], will administer a patient satisfaction survey. Once the survey is collected, the subject's participation in the study will cease.

All photographs will be uploaded to a hospital-provided Box.com account. Photograph files will be named in the following format: "001pre.xxx" or "001post.xxx," such that the "001" portion indicates study subject number, and the "pre" or "post" indicates when the photograph was taken ("pre" indicates that the photograph was taken prior to application of the EyeGard®/Tegaderm™, post indicates that the photograph was taken after removal of the EyeGard®/Tegaderm™). The "xxx" indicates the file format in which the photograph is saved.

The Box.com folder containing the photographs will be shared with the dermatologists who will evaluate the degree of erythema. The dermatologists will be asked to evaluate the erythema based on the following tape-associated skin index grading scale:

Erythema assessment:

0 - no visible erythema

1 - mild erythema

2 - moderate erythema

3 - severe erythema

Each dermatologist will be given a "Dermatologist Evaluation Sheet" which will list all of the photographs that are to be evaluated. He or she will independently evaluate each photograph.

Once all dermatological evaluations of the photographs are complete, the results will be compared. Should there be inconsistency in the Grade rating, the majority (two out of three) will be counted.

If the EyeGard® and/or Tegaderm™ fall off prior to the end of surgery, a photograph will be taken at that time and the time duration noted. Afterwards, a new tape will be re-applied.

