8.1 Study Endpoints

Primary endpoint: immediately upon removal of Tegaderm™ and EyeGard®

Secondary endpoint: post-operative day 1 when patient satisfaction data is acquired

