8.4 Data Management

The data to be collected will be divided into two general groups: (1) Paper forms, such as the consent forms and data collection sheets, will be stored in the principal investigator's locked office. (2) Digital form, such as the data collection excel spreadsheet which includes the following variables: Subject ID, R and L eye tape assignments, length of surgery, R and L eye pre-op photo numbers, R and L eye pre-op scores (from three dermatologists), R and L eye post-op photo numbers, R and L eye post-op scores (from three dermatologists), final erythema score (post minus pre), patient satisfaction with R eyelid condition, patient satisfaction with L eye condition, and additional notes, will be stored on a Tufts Medical Center provided, password protected, encrypted, Box storage account, which is compliant with institutional policies regarding HIPAA and the IT department. (3) All photos will also be stored on Box.com.

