8.5 Randomization

Will subjects be randomized?

Yes No

In order to randomly allocate study subjects to one of three arms entirely by chance, we will use the on-line randomization tool "Research Randomizer Version 4.0, www.randomizer.org," which is a computer-based "random number generators," the numbers are generated by use of a complex algorithm (seeded by the computer's clock) that gives the appearance of randomness. This tool has been studied and validated as an adequate randomization tool, to generate a randomization list. Allocation concealment will be maintained by preparing sequentially numbered, sealed, opaque envelopes, which will contain the randomization assignment consistent with the generated randomization list.

The following strategies will be implemented in order to ensure blinding:

- (a) When a subject enrolls in the study, the co-investigator, [name], will open the envelope with randomization number inside. [name] will be the one to apply and remove the tapes. Once the tapes are removed, a second set of photographs will be taken. The dermatologists who will be in charge of determining the primary outcome (erythema score) will not be present during any part of the procedure.
- (b) The photos will only be linked to the experimental variable (tape type) by the data collection spreadsheet that is only accessible to the principal investigator, [name], and the co-investigator, [name]. After data collection for the study is complete, the photos will be presented to the dermatologists independently in a blinded manner.
- (c) Each dermatologist's grading will subsequently be recorded in the data collection spreadsheet by the co-investigator. Therefore, the dermatologist will have no opportunity to determine the type of tape used at any point during the study.
- (d) Study subjects will not be informed of which tape is assigned to which eyes, and the tape will be applied and removed while the patient is under anesthesia. Therefore, the patient will be blind to the type of tape used throughout the course of the study, including when he/she is reporting his/her satisfaction with post-operative eyelid condition.

9 Drugs or Devices

Will the research involve drugs?

Yes No

Will the research involve devices?

Yes No

10 Study Administration

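### A photograph taken when one tape falls off can show the grading dermatologists the other eye's tape, contrary to the blinding statement in 8.5(c)

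*Combined protocol and SAP*

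**What the plan says.** Each patient receives Tegaderm on one eye and EyeGard on the other. Three dermatologists grade erythema from photographs, and the majority grade counts.

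- **Early loss of tape (5.2).** The rule covers loss of either tape or both: "a photograph will be taken at that time and the time duration noted. Afterwards, a new tape will be re-applied".
- **Framing (5.2).** "The photographs will be taken and cropped in such a way that both eyelids are visible". No other framing is given for a fall-off photograph.
- **Storage and access (5.2).** Every photograph is uploaded, with a file name made of the subject number and either pre or post. "The Box.com folder containing the photographs will be shared with the dermatologists who will evaluate the degree of erythema".
- **Blinding (8.5).** Item (b) says that only the data collection spreadsheet links photographs to tape type. Item (c) concludes that "the dermatologist will have no opportunity to determine the type of tape used at any point during the study".
- **Outcome photograph.** Section 3 and 5.1 place it at the end of surgery. In 5.2, after the co-investigator removes both tapes at that point, "She will then take another photograph of the eyelids and document the time". Section 8.1 reads "Primary endpoint: immediately upon removal of" the two products, and 8.5(a) says "Once the tapes are removed, a second set of photographs will be taken". The spreadsheet in 8.4 has one set of "R and L eye post-op scores (from three dermatologists") and no field for a fall-off photograph.

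**The concern.** The endpoint is a visual grade, and the person who applies the tapes, removes them and takes the photographs knows the allocation. Masking of the dermatologists is therefore the main protection against assessment bias. Section 8.5(c) states that masking without exception, but 5.2 creates a photograph that can defeat it.

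What is at stake is the grading of the affected patients. Both eyes of a patient are compared with each other, so a grader who knows one assignment knows both sides of that pair. The documents give no basis for predicting which way a grader would lean.

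A smaller gap goes with this. The plan requires the fall-off photograph and the tape time but does not say what either is for.

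**Working it through.** The main check is textual.

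**How the tape becomes visible**

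1. The fall-off rule in 5.2 covers loss of one tape alone. The fellow eye is then still taped when the photograph is taken.
2. The framing rule in 5.2 puts both eyelids in the picture, so the remaining tape is in view.
3. The upload rule in 5.2 covers all photographs, and the folder is shared with the graders. No passage masks, crops or withholds a fall-off photograph.
4. Each patient has one product per eye. Recognising the tape on one eye gives the assignment of the other by elimination.
5. The file name carries the subject number, so what is seen in the fall-off photograph can be carried over to the same subject's post photograph. This holds even if the fall-off photograph is never graded.
6. Such a photograph is itself a link between picture and tape type. The premise in 8.5(b), that the spreadsheet is the only link, then fails for that subject, and so does the conclusion in 8.5(c).

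Step 4 needs the two products to be distinguishable in a photograph. The documents do not say whether they are.

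**How many patients**

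Section 8.3 gives 144 pairs and a 10% allowance: 144 × 1.10 = 158.4, rounded up to the stated 159. The documents give no fall-off rate, so the rates below are assumptions.

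| Assumed share with one-eye fall-off | Share × 159 | Patients, about |
|---|---|---|
| 1% | 1.6 | 2 |
| 5% | 8.0 | 8 |
| 10% | 15.9 | 16 |
| 20% | 31.8 | 32 |

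These are patients whose assignment could be seen, not patients whose grade would change. One changed binary grade for one eye moves the paired difference by 1/144 = 0.69 percentage points. One grader can change the majority only when the other two disagree.

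**Which photograph is the outcome**

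After fall-off a new tape is applied, and that tape is removed at the end of surgery. The photograph taken then meets section 3, 5.1 and the end-of-surgery step in 5.2. It also meets 8.1 and 8.5(a), which speak of removal of both tapes. A one-eye fall-off photograph does not meet 8.1 or 8.5(a), because the fellow tape is still on. The end-of-surgery photograph therefore fits every passage. What is missing is a sentence on how the fall-off photograph is used.

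**The case against.** **Several things must coincide.** One tape alone must fall off, the photograph must show both eyes and reach the shared folder, the products must be recognisable, and a grader must notice and connect the files. This stands as a limit on size. The second and third conditions, however, are what 5.2 prescribes.

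**The plan has other safeguards.** Section 5.2 gives each dermatologist a sheet listing the photographs to grade, and 8.5(b) says the photographs are presented independently and blinded. Section 8.4 has separate photo numbers for the right and left eye, which might suggest single-eye images. None of these closes the gap. The sheet determines what is graded, not what the folder contains. Section 8.5(b) states an aim without a step that would hide a visible tape. The photo numbers do not override the framing rule.

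**A reader might infer that the plan prescribes two different outcome photographs after fall-off.** The documents do not support that. Section 5.2 calls the early event a fall-off, not a removal, and never calls its photograph the outcome. The end-of-surgery photograph satisfies all the timing statements.

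**A reader might also infer that the team could choose between photographs once grades are known.** That would require both to be graded. No passage says so, and 8.4 has room for only one set of post-operative scores per eye.

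**Conclusion.** The contradiction between the photograph handling in 5.2 and the unqualified statement in 8.5(c) is real, provided the two products can be told apart in a photograph. It is confined to patients in whom one tape falls off while the other stays on. Their number cannot be derived from the documents and is probably small. Neither the size nor the direction of any bias can be given. The documents do not support reading this as a general failure of masking or as a threat to the main conclusion.

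The unstated use of the fall-off photograph is a point of clarification only. This is an optional improvement, worth making because it costs almost nothing and removes an exception to the masking.

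**What to change.** - **In 5.2 and 8.5:** keep any fall-off photograph out of the graders' folder. Alternatively, crop it to the uncovered eyelid and give it a file label of its own that does not link it to the subject's post photograph.
- **In the same sentence:** confirm that the end-of-surgery photograph supplies the primary grade, as section 3 and 5.2 already indicate. State that the fall-off photograph is used only in a sensitivity analysis, with tape times reported.

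The rules on re-application and on removal for safety stay as they are. If the fall-off photograph is withheld during primary grading, the cropped version can be graded afterwards for the sensitivity analysis.

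The cost is a little file handling and no extra visit or patients. One downside should be acknowledged: the primary grade of a re-taped eye reflects two applications, which is why tape times should be reported.

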5.3 Evaluations

Will you perform any laboratory tests for this study?

Yes No

5.4 Collection and Storage of Human Biological Specimens (Tissue Banking)

Will biological specimens be stored for **future, unspecified**, research?

Yes No

6 Ethics and Protection of Human Subjects

6.1 Informed Consent Process

Will subjects be required to provide informed consent?

Yes No

- The informed consent will take place in the pre-operative area in the patient's individual holding bed, the same location where surgical and anesthesia consent is performed as well.
- The patient will have one hour before the start of the procedure to make a decision regarding enrollment.
- The consent will be obtained in person and documented in writing according to SOP: Informed Consent Process for Research (HRP-090)

- Non-English speakers will be enrolled using interpreters and IRB approved Short Forms per the IRB's Short Form policy

6.2 Waiver or Alteration of Consent Process

- Is a waiver or alteration of the consent process being requested for this study?
 Yes No
- Is a waiver of the consent process being requested for parents for research involving children?
 Yes No
- Is a waiver of the consent process for planned emergency research being requested?
 Yes No

6.3 Confidentiality

In order to maintain confidentiality, the following measures will be taken:

- All study related materials will be stored in a secure location. The consent forms and other paper forms (e.g. data collection sheet) will be stored in the principal investigator's locked office. All digital files (e.g. excel forms, photography) will be stored on a Tufts Medical Center provided, password protected, encrypted, Box storage account, which is compliant with institutional policies regarding HIPAA and the IT department.
- The principal investigator and co-investigators will have exclusive access to the forms.
- Records will be stored for 7 years after the study is closed with the IRB, as per IRB policy.
- A certificate of confidentiality will not be obtained.

6.4 Provisions to Protect the Privacy Interests of Subjects

Subjects will be assured that their contact with any member of the research team is optional, and that the information they share will be strictly confidential.

6.5 Provisions to Monitor the Study to Ensure the Safety of Subjects

- This study does not pose any additional safety risks beyond those associated with the application of protective tape over the patient's eyelids that occurs during standard surgical procedures. These risks include injury to the eyelid such as mild to severe erythema, edema, and abrasion. Patient safety is a top priority. If at any time a patient's safety is threatened during that patient's participation in this study, for example in the event that a patient has an allergic reaction to the tape or perhaps an unrelated surgical complication necessitates the removal of the tape, the tape will be removed and the patient will not complete his/her participation in the study.
- No Data and Safety Monitoring Board will be used in this study.

6.6 Compensation for Research-Related Injury

Does the research involve greater than minimal risk to subjects?

- Yes No

6.7 Economic Burden to Subjects

Does the research involve any costs to subjects?

- Yes No

6.10 Vulnerable Populations

Will pregnant women be enrolled?

Yes No

Will the research involve neonates of uncertain viability or non-viable neonates?

Yes No

Will subjects who are not yet adults (neonates, children, teenagers) be enrolled?

Yes No

Will minors who are:

- i) married, widowed, divorced; or
- ii) the parent of a child; or
- iii) a member of any of the armed forces; or
- iv) pregnant or believes herself to be pregnant; or
- v) living separate and apart from his/her parent or legal guardian, and is managing his/her own financial affairs

be approached for study participation for either themselves or their child?

Yes No

Will wards of the state and/or children at risk of becoming wards of the state be enrolled (this includes foster children or any child that is in state custody)?

Yes No

Will cognitively impaired adults (adults with impaired-decision making capacity) or adults who may lose the capacity to consent be enrolled?

Yes No

Will prisoners be enrolled?

Yes No

Will students and/or employees be enrolled in this research?

Yes No

7 Adverse Event Monitoring

7.1 Definitions

The study does not carry a higher risk of adverse events than typically expected from the use of tape over the eyelids during surgical procedures. Possible adverse events may include allergic reaction to the tape and abrasion caused by tape removal.

Adverse event: An adverse event is any untoward or unfavorable medical occurrence in a human subject, including any abnormal physical exam or laboratory finding, symptom, or disease, temporally associated with a subject's participation in the research.

Serious adverse reaction: a serious medical occurrence associated with the use of TegadermTM, or EyeGard[®] such as life-threatening allergic reaction.

Unanticipated problems: any incident, experience, or outcome that meets **all** of the following criteria: unexpected; related or possibly related to participation in the research; and suggests that the research places subjects at a greater risk of harm than was previously known or recognized.

7.2 Reporting Procedures

Patients are routinely monitored for development of adverse events as part of their anesthetic care. This occurs on a continuous basis from the moment the anesthetic is administered until the moment the patient is

discharged home. A computerized system exists which alerts clinicians to the development of some adverse effects, and is recorded in the medical record. The co-investigator, [name], will be alerted in these situations and all adverse events will be forwarded to the principal investigator. Clinicians are alerted to events immediately as they occur. Clinical staff are trained to deal with such events. The co-investigator, [name], will be responsible for contacting the principal investigator to report the occurrence of adverse events. The principal investigator will then complete any necessary safety forms, include the Anesthesia Department's Quality Assurance form. The events will be reported within 24 hours to the QI director and the Chairman of the department, and to the IRB within 5 days.

7.3 Reportable New Information

Reportable new information will be reported to the IRB per the Tufts Health Sciences IRB's "Reportable New Information policy". The PI will submit any updated information that may affect the conduct of this study or subject safety, rights, welfare or willingness to take part in the research.

8 Statistical Considerations

